## 10.2 Supply, Packaging, Labelling, Handling and Storage

DS107 cream and vehicle cream will be provided by the Sponsor.

The DS107 cream and vehicle cream will be a white to off white-cream formulation supplied from the manufacturer to the central distribution facility. The central distribution facility will supply the IMP and vehicle to site where it will be handled by the site pharmacy or responsible personnel according to local Regulations. Patients who qualify for randomisation at Baseline/Visit 2 will be given IMP for 2 weeks/14 days at Baseline/Visit 2, Week 2/Visit 3, Week 4/Visit 4, and Week 6/Visit 5.

The DS107 cream and vehicle cream will be labelled with information according to local regulation.

The study medication will be provided by the Sponsor to the Investigator and will be kept, on site, in a locked room or cabinet with limited access. The DS107 cream and vehicle cream will be stored at a controlled room temperature of ambient condition (ie. Up to 25°C) in a secure area protected from unintended use and will only be supplied to patients in the trial under the supervision of the Investigator.

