2.2.13.1 Extent of Exposure

Treatment duration is defined as 8 weeks (Day 56 \pm 2 days). The date of the first and last applications of study medication will be collected from information recorded on the study drug admin page of the eCRFs. Study medication is to be applied twice daily.

Extent of exposure to study medication will be tabulated by treatment group by 2-week intervals. The number of applications of study medication will be summarized by treatment group by each 2-week interval only for those subjects who returned to the clinic for each interval. The expected number of applications per 2-week intervals is 14, based on twice daily dosing. Compliance will be measured by calculating the number of applications/expected number of applications *100 and presented by treatment group for each interval.

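### Applications are counted only among patients who returned for the interval, and no by-arm summary of time on treatment or total applications covers the whole safety set

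*SAP*

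**What the plan says.** SAP 2.2.13.1 tabulates extent of exposure by arm in two-week intervals. The application count is given "only for those subjects who returned to the clinic for each interval". The compliance rule follows: "Compliance will be measured by calculating the number of applications/expected number of applications *100 and presented by treatment group for each interval". Its denominator is also stated: "The expected number of applications per 2-week intervals is 14, based on twice daily dosing".

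On duration the section says "Treatment duration is defined as 8 weeks", with a window of two days either side of Day 56. It adds that "The date of the first and last applications of study medication will be collected" from the eCRF. It specifies no summary of days between those dates and no total of applications over the treatment period. It also gives no rule for patients who do not return, or for those who have stopped the cream but still attend.

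SAP 2.2.13 defines the safety population as everyone enrolled who received at least one dose.

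**The concern.** An exposure table should say how much product each arm received. Once the count is limited to patients who returned, exposure is described only for those still attending. A patient who leaves drops out of both numerator and denominator of every later interval. If one concentration loses more patients than another, the interval tables need not show it.

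This matters for the safety objective. SAP 2.2.13.3 reports adverse events as counts and percentages of patients with Fisher exact tests, without adjustment for time on treatment. To judge whether a low percentage reflects good tolerability or short exposure, a reader needs time on treatment by arm for the same population as the adverse-event tables. SAP 2.2.6 also separates an effect under full adherence from one that allows for discontinuation, and actual exposure by arm helps to interpret both.

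The wording also has a stricter reading: returning for each interval could mean attending all of them, in which case a leaver's earlier applications would be lost too.

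**Working it through.** **Inputs**
- Frequency: "Study medication is to be applied twice daily" (SAP 2.2.13.1).
- Interval length: patients "will be given IMP for 2 weeks/14 days at Baseline/Visit 2, Week 2/Visit 3, Week 4/Visit 4, and Week 6/Visit 5" (protocol 10.2), so four intervals of 14 days.
- Planned period: 56 days. Two applications fall on Day 0, and the last is on the evening before Visit 6 (protocol 8.2.3 and 8.2.7).
- Dropout and adherence: the documents give neither. All rates below are assumptions.

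**1. The plan's own figure.** Expected applications per interval = applications per day x days = 2 x 14 = 28. The SAP states 14, which does not reproduce. Over eight weeks the schedule gives 2 x 56 = 112, against 4 x 14 = 56 implied by the SAP. With 14 as denominator, a patient who applies everything scores 28/14 = 200%, and a score of 100% means half the scheduled applications. The steps below use the stated twice-daily schedule as a working basis. The percentages in steps 2 and 3 do not depend on that choice, because the per-interval count cancels.

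**2. Patients stop and leave.** Assume perfect application until stopping, with every stopper leaving on an interval boundary. Returners then read 100% in every interval. For all treated patients:
- 20% leave at Day 28: (0.8 x 112 + 0.2 x 56)/112 = 100.8/112 = 90.0%.
- 30% leave at Day 14: (0.7 x 112 + 0.3 x 28)/112 = 86.8/112 = 77.5%.

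**3. The same patients stop but keep attending.** If the 20% who stop at Day 28 still come to visits and count as zero, the four intervals read 100, 100, 80 and 80%. Their mean is 90%, equal to the all-treated figure, so the gap is zero.

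**4. Two arms with different losses.** Assume 95% adherence while on treatment, loss at a constant rate per interval, and nothing counted from the interval of non-return. With cumulative loss d by Week 8, mean applications per treated patient = 0.95 x 28 x [(1-d)^(1/4) + (1-d)^(2/4) + (1-d)^(3/4) + (1-d)].

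| Loss by Week 8 | Returners, each interval | Mean applications, all treated | Share of 112 |
|---|---|---|---|
| 10% | 95% | 99.7 | 89.0% |
| 30% | 95% | 85.6 | 76.4% |

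The two arms look identical in the returner table. If leavers are credited with half of their last interval, the all-treated figures become 90.2% and 80.0%.

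**5. Denominator for the whole period.** Visit 6 may fall on Day 54 to Day 58 (protocol Appendix 1). A fully compliant completer then makes 2 x 54 = 108 to 2 x 58 = 116 applications. Against a fixed 112 that scores 96% to 104%, so completers need a denominator based on their actual Visit 6 date.

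**The case against.** The strongest reply is that the restriction sits in one sentence, on application counts. Neither the sentence that tabulates extent of exposure nor the compliance sentence carries it. That is correct: extending it to compliance is an inference. It is the natural one, because the SAP names no other source of application counts.

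Second, not every early stopper is lost. Protocol 7.5.2 keeps patients withdrawn from the cream in follow-up. Protocol 7.5 asks those leaving the study to attend a termination visit, where the log is reviewed (8.2.7). This stands and limits the size of the gap, as step 3 shows. The SAP still does not say how either group is counted.

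Third, a reader might infer that every arm will look almost fully treated. That does not follow: returners who apply 80% of the cream would show 80% against a denominator of 28, and with the written 14 full application would show 200%. The selection hides attrition, not poor adherence among attenders.

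Fourth, a reader might infer that differential stopping would be invisible. It would not. SAP 2.2.2 tabulates visit attendance and withdrawals with reasons by arm. SAP 2.2.13.3 tabulates adverse events leading to dose changes or drug withdrawal. SAP 2.2.3 and 2.2.13.3.3 add listings of medication use and dosing changes. What none of these gives is a by-arm summary of days or applications received.

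Finally, the eight-week definition might be taken to assign eight weeks to everyone. It reads better as the planned period: SAP 2.2.5 says treatment ends earlier for those who discontinue.

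**Conclusion.** The point holds as a reporting gap. The application count, and by natural reading the compliance built on it, is conditional on attendance, and no by-arm summary of time on treatment or total applications is specified for the whole safety set. Arms with different attrition can therefore show the same compliance.

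Under the assumed patterns in step 2, the overstatement is 10 points (20% leaving at Day 28) to 22.5 points (30% leaving at Day 14). It is zero if everyone who stops keeps attending and counts as zero. The true size cannot be fixed from the documents. The effect is on the interpretation of exposure and safety; no hypothesis test on efficacy uses these figures. The mismatch between 14 and twice-daily application is certain, and affects every compliance figure until it is resolved.

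**What to change.** Reconcile the expected count of 14 per two weeks with the twice-daily schedule before any compliance figure is computed. Then amend SAP 2.2.13.1 as follows.

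- For all patients in the Safety Analysis Set, report by arm the days from first to last application (last minus first plus 1).
- For the same patients, report whole-period applications and compliance against the planned twice-daily applications. Use the actual Visit 6 date for completers and the planned 56 days for early stoppers. Count zero after the last application date, and show unreturned logs as unknown.
- Keep the by-interval table, with the number returned over the number treated beside each interval.
- State that patients off the cream who still attend count as zero.
- State whether returning for each interval means that interval or all of them.

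The cost is SAP wording and one more table, largely from data already collected. Reported compliance will be lower than among returners alone. It is best settled before unblinding.

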### **8.2.2 Treatment Period**

Following completion of a successful screening visit, patients will begin the comparative treatment period (8 weeks).

At the start of the comparative treatment period, after confirmation of continued eligibility, patients will be randomly assigned at the baseline visit (Visit 2) to one of the three treatment regimens.

Patients will be instructed to apply DS107 cream or vehicle cream in the morning and in the evening (except on the mornings of clinic visits when patients will be instructed to abstain from applying DS107/vehicle cream prior to the visit. They will apply DS107/vehicle cream as soon as all of the efficacy assessments are complete during the clinic visit). Each self-administration of IMP will be recorded in a patient compliance log.

Unscheduled visits may occur when a patient needs to make a visit in between the scheduled visit dates due to an AE, difficulty complying with the study protocol requirements, or a significant change in their disease state. All procedures that are medically necessary should be followed.

Patients who discontinue the study early will have all study procedures scheduled for Visit 6 (see Section 8.2.7) performed as soon as possible after patient withdrawal so that all study-related information can be recorded.

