### 8.2.3 Baseline (Visit 2)

Patients will attend the investigational site at Visit 2 when the following procedures/assessments will occur.

- Verification of inclusion/exclusion criteria (Sections 7.2 & 7.3)
- Hanifin and Rajka criteria review (as detailed in Section Appendix 2 (15.2))
- Patient randomisation (as detailed in Section 10.5)
- Samples for clinical laboratory safety tests (haematology, urinalysis and serum biochemistry as detailed in Section 9.2.4)
- Biomarker sampling (as detailed in Section 9.2.6)
- Vital signs (blood pressures, heart rate and body temperature), as detailed in Section 9.2.3)
- Physical examination (as detailed in Section 9.2.2)
- Dispense study drug
- Dispense patient compliance log
- Study drug administration (on site) (as detailed in Section 10.3)
- Investigator's Global Assessment (IGA) (as detailed in Section 9.1.1)
- Body Surface Area (BSA) (as detailed in Section 9.1.4)
- Eczema Area and Severity Index (EASI) (as detailed in Section 9.1.2)
- NRS pruritus assessment (as detailed in Section 9.1.3)
- Dermatology Life Quality Index (DLQI) Questionnaire (as detailed in Section 9.1.5)
- Patient Orientated Eczema Measure (POEM) (as detailed in Section 9.1.6)
- Patient Global Impression of Severity Questionnaire (PGI-S) (as detailed in Section 9.1.7)
- Patient Global Impression of Change Questionnaire (PGI-C) (as detailed in Section 9.1.8)
- Concomitant medication assessment (as detailed in Section 9.2.9)

If all study entry criteria are satisfied the Investigator will randomize the patient and provide the patient with six tubes of the designated DS107 or vehicle cream from one of the patient treatment packs available at the site (allocated via the central randomization).

The first application of DS107 or vehicle cream will be carried out at site once all baseline assessments have been completed. The patient will carry out their second application of DS107 or vehicle cream in the evening of Day 0.

Patients will be given a compliance log to document application of the DS107 or vehicle cream. Clinical staff will explain to the patient how to use the compliance log to document IMP application compliance.

**All dispensed DS107 cream and vehicle cream should be weighed (tube only, without the outer carton but including the tube lid) upon dispensing.**

An NRS for the assessment of pruritus will be captured on a daily basis from baseline through to the follow up visit.

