## 10.3 Dosage and Administration

IMP at dose strengths of 5% and 1% DS107 cream or vehicle cream will be topically applied liberally to all affected or commonly affected areas twice daily (morning and evening) by the patients. **The last study drug application should occur on the day preceding Week 8 (Visit 6) /early termination (ET) visit.** Patients will be randomized to one of the three treatment groups in a 1:1:1 ratio:

- Treatment group A: 1% DS107 cream applied topically to all affected or commonly affected areas twice-daily for 8 weeks

- Treatment group B: 5% DS107 cream applied topically to all affected or commonly affected areas twice-daily for 8 weeks
- Treatment group C: Vehicle cream applied topically to all affected or commonly affected areas twice-daily for 8 weeks

An area for treatment will be defined at study start and DS107 or vehicle cream will be applied to all that area (and any newly affected areas) for the complete 8 week duration. Emollients can be applied to other areas of dry skin not in the defined treatment area.

DS107 or vehicle cream will not be applied on the morning of clinic visits 3, 4, 5, and 6 (will be applied as soon as all of the efficacy assessments are complete during the clinic visit). To maintain the blind throughout the study, the DS107 cream and vehicle cream will be identical in appearance.

If a patient misses one application of the study product they should apply the study product as usual at the time of the next scheduled application. Patients should remember to note the missed application in the Patient Compliance Log.

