#### **10.4 Duration of Treatment**

Patients will topically apply either DS107 cream or vehicle cream liberally to all affected or commonly affected areas twice daily for 8 consecutive weeks.

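### The SAP's compliance denominator of 14 applications per 2-week interval should be 28, so every reported compliance percentage is doubled

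*SAP*

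**What the plan says.** SAP section 2.2.13.1 gives the dosing frequency ("Study medication is to be applied twice daily"), then the expected count ("The expected number of applications per 2-week intervals is 14, based on twice daily dosing"), then the formula: "Compliance will be measured by calculating the number of applications/expected number of applications *100 and presented by treatment group for each interval". SAP section 2.1 plans to show compliance by arm for mild AD, moderate AD and the two combined.

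The protocol agrees on the frequency. Section 10.3 has the cream "topically applied liberally to all affected or commonly affected areas twice daily (morning and evening) by the patients", and section 10.4 repeats it: "liberally to all affected or commonly affected areas twice daily for 8 consecutive weeks". On interval length, section 10.2 says that randomised patients "will be given IMP for 2 weeks/14 days at Baseline/Visit 2, Week 2/Visit 3, Week 4/Visit 4, and Week 6/Visit 5". The counting unit is the single application. Section 8.2.2 says "Each self-administration of IMP will be recorded in a patient compliance log", and section 10.3 asks patients to note a single missed application in the same log.

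**The concern.** The stated basis and the stated count contradict each other within one sentence, and that count is the denominator of the only compliance measure the SAP defines. Programmed as written, the rule makes every percentage in a planned display wrong.

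The practical danger is that the wrong values can look right. An arm or subgroup at about half use would show about 100%, which invites no query. A mix of good and poor users would average above 100%, which can hide the under-use. Adherence also bears on interpretation: SAP section 2.2.6 describes the effect under the primary missing-data assumption as the one that full adherence to treatment would give. A reader weighing that description needs an adherence figure that means what it says.

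**Working it through.** **Inputs**

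- Frequency: 2 applications per day (SAP 2.2.13.1; protocol 10.3 and 10.4).
- Nominal interval: 14 days (protocol 10.2).
- Unit: one self-administration (protocol 8.2.2).
- Start: two applications on Day 0, the first on site and then "The patient will carry out their second application of DS107 or vehicle cream in the evening of Day 0" (protocol 8.2.3).
- Visit days: at Visits 3 to 5 the morning application is delayed until the efficacy assessments are done, not dropped (protocol 10.3).
- End: the last application is on the day before the Week 8 visit (protocol 10.3), so dosing covers Days 0 to 55, which is 56 days.
- Visit windows: ±2 days at Weeks 2, 4, 6 and 8 (SAP 2.2.5).

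**Can the stated 14 be reproduced?** Expected count = applications per day × days in the interval.

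- Twice daily, 14 days: 2 × 14 = 28. Not 14.
- The same, if one visit-morning application were lost: 28 − 1 = 27. Not 14.
- Once daily, 14 days: 1 × 14 = 14. This contradicts the twice-daily frequency.
- Twice daily, 7 days: 2 × 7 = 14. This contradicts the 2-week interval.

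Over the whole treatment period, 2 × 56 = 112 applications are expected, or 112 / 4 = 28 per interval. The SAP figure implies 4 × 14 = 56.

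**Effect on the percentage.** Compliance = applications / expected × 100, for a nominal 14-day interval:

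| Applications made | With 14 (as written) | With 28 |
|---|---|---|
| 28 (full use) | 200.0% | 100.0% |
| 21 | 150.0% | 75.0% |
| 14 (half use) | 100.0% | 50.0% |
| 7 | 50.0% | 25.0% |

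**Visit windows, a separate matter.** The first interval starts at a fixed Day 0 and ends at Day 14 ± 2, so it lasts 12 to 16 days, or 24 to 32 applications. Later intervals have a movable visit at each end and can last 10 to 18 days, or 20 to 36 applications. A perfectly adherent patient would then read as follows:

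| Interval | Against 14 | Against a fixed 28 |
|---|---|---|
| First (24 to 32) | 171.4% to 228.6% | 85.7% to 114.3% |
| Later (20 to 36) | 142.9% to 257.1% | 71.4% to 128.6% |

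A fixed 28 is therefore right for the nominal interval. In an individual case it can be off by up to 2 days (4 applications) in the first interval and up to 4 days (8 applications) in later ones.

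**The case against.** The best defence accepts the arithmetic and disputes the consequence. The error is a constant factor of 2, the same in every arm. It preserves the ranking of patients and the ratio between arms, and halving the value undoes it exactly. SAP 2.2.13.1 also summarises the raw number of applications, which needs no denominator, and SAP 2.2.3 provides a subject listing of medication use. Sites review the compliance log at each return visit during treatment, and tubes are weighed. Arm-level values near 200% would be noticed. All of this stands, and it limits the harm.

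It also rules out several stronger conclusions that a reader might draw:

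- **That the per-protocol set will be wrong.** Protocol 12.7 and SAP 2.2.4.3 define the set by study completion and absence of major violations, judged patient by patient at a blinded meeting. Neither gives a compliance cut-off or names this percentage as an input. The most that can be said is that the percentage would mislead that meeting if it were used.
- **That poor compliance cannot be detected, or a null result cannot be explored.** The raw counts and the listing remain available.
- **That a patient who used half the cream looks fully compliant.** The measure counts applications. Application is liberal with no fixed amount, and quantity is followed separately by tube weight.

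None of this makes 14 correct. An arm at half use would show a plausible 100%, which does not announce itself as an error.

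**Conclusion.** The point holds: the expected count should be 28, and as written every compliance percentage is twice its value on that base, in every interval and arm. The factor is exact against the nominal 14-day interval. With actual visit dates, full use could read anywhere from about 143% to 257%.

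This rests on counting each self-administration as one application, as the protocol's log does, and on visit-morning applications being delayed and not lost. Losing one would give 27, which leaves the conclusion unchanged. Nothing in either document redefines an application as a treatment day.

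The scope is the descriptive exposure and compliance displays. The primary analysis does not use the percentage, and no stated population definition does. It is a clear error that should be corrected before the tables are programmed, but it does not threaten the trial's efficacy conclusions.

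**What to change.** In SAP 2.2.13.1, replace 14 with 28 so that the count matches the SAP's own twice-daily basis. The cost is one line of text and one programming constant, and no clinical rule changes.

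As an optional refinement for the visit windows, define the denominator as 2 × the scheduled dosing days between the actual visit dates. Say explicitly that days with no application stay in the count; otherwise the wording could be read as counting only days of use, which would inflate compliance. Each interval should run from its opening visit to the day before its closing visit, so that the last one ends the day before the Week 8 visit. This uses visit dates already collected and adds a short derivation to the program.

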#### **8.2.4 Week 2 (Visit 3)**

Patients will return to the investigational site at Week 2/Visit 3. Patients should not apply DS107 or vehicle cream on the morning of Visit 3.

For accountability purposes, patients will be required to bring both the used and unused DS107/vehicle cream supplied at Visit 2. Patients will be required to provide the patient compliance log for confirmation of compliance.

The following procedures/assessments will occur:

- Vital signs (blood pressures, heart rate and body temperature), as detailed in Section 9.2.3)
- Physical examination (as detailed in Section 9.2.2)
- Dispense study drug
- Collect study drug

- Dispense patient compliance log
- Collect and review patient compliance log
- IMP accountability (as detailed in Section 10.6)
- Study drug administration (on site) (as detailed in Section 10.3)
- Investigator's Global Assessment (IGA) (as detailed in Section 9.1.1)
- Body Surface Area (BSA) (as detailed in Section 9.1.4)
- Eczema Area and Severity Index (EASI) (as detailed in Section 9.1.2)
- NRS pruritus assessment (as detailed in Section 9.1.3)
- Dermatology Life Quality Index (DLQI) Questionnaire (as detailed in Section 9.1.5)
- Patient Orientated Eczema Measure (POEM) (as detailed in Section 9.1.6)
- Patient Global Impression of Severity Questionnaire (PGI-S) (as detailed in Section 9.1.7)
- Patient Global Impression of Change Questionnaire (PGI-C) (as detailed in Section 9.1.8)
- Concomitant medication assessment (as detailed in Section 9.2.9)
- AE assessment (as detailed in Section 11)

The DS107 or vehicle cream will be returned and six tubes of DS107 or vehicle cream will be supplied to the patient. The cream will continue to be applied twice-daily. The patient compliance log will be provided to the patient who will be instructed to complete this as before.

**All dispensed DS107 cream and vehicle cream should be weighed (tube only, without the outer carton but including the tub lid) upon dispensing and again upon return of product.**

An NRS for the assessment of pruritus will continue to be captured on a daily basis from baseline to the follow up visit.

On completion of this visit, patients will be advised that they will be required to return to the investigational site at Visit 4 and to bring with them the unused DS107/vehicle cream, the used DS107/vehicle cream, and the patient compliance log. Patients should not apply DS107 or vehicle cream on the morning of their return site visit (Visit 4).

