2.2.5 Study Assessment Time Points

The study consists of seven protocol-specified visits which will be assessed as nominal visits from an analysis perspective:

- Visit 1/Screening visit (Day -30 to -1): Once informed consent has been obtained, the Investigator will assign a Patient Number and the subject will undergo the screening procedures. Following completion of a successful screening visit, patients will begin the comparative treatment period (8 weeks).
- Visit 2/Baseline (Day 0): At the start of the comparative treatment period, after confirmation of continued eligibility, patients will be randomly assigned to one of the three treatment regimens. Study medication is dispensed at Visit 2. The first application of study medication will be carried out at the site once all baseline assessments have been completed. The patient will carry out their second application of study medication in the evening of Day 0.
- Visits 3, 4 and 5: Follow-up visits at Week 2 (Day 14 ± 2 days), Week 4 (Day 28 ± 2 days) and Week 6 (Day 42 ± 2 days) respectively.
- Visit 6 – End of Treatment (EOT): Week 8 (Day 56 ± 2 days) for subjects who complete 8 weeks of treatment; earlier for subjects who discontinue treatment prematurely.
- Visit 7/Week 10: End of Study visit (Day 70 ± 3 days) for all subjects.
- Unscheduled Visits: Unscheduled visits may occur when a patient needs to make a visit in between the scheduled visit dates due to an AE, difficulty complying with the study protocol requirements, or a significant change in their disease state. All procedures that are medically necessary should be followed.

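### Compliance uses a fixed count per 2-week interval, so a fully adherent patient's per-interval figure moves with visit timing and early stopping, even at two applications per day

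*SAP*

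**What the plan says.** SAP 2.2.13.1 (Extent of Exposure) gives the regimen, "Study medication is to be applied twice daily", and then one constant for the denominator: "The expected number of applications per 2-week intervals is 14, based on twice daily dosing". Applications are summarised "only for those subjects who returned to the clinic for each interval". The measure itself is then defined: "Compliance will be measured by calculating the number of applications/expected number of applications *100 and presented by treatment group for each interval". No overall per-patient figure is specified. SAP 2.1 adds that compliance will be shown for mild, moderate and combined disease.

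The timing comes from SAP 2.2.5, which places the visits at "Week 2 (Day 14 ± 2 days), Week 4 (Day 28 ± 2 days) and Week 6 (Day 42 ± 2 days) respectively". Visit 6 is at Day 56 ± 2 days for completers and "earlier for subjects who discontinue treatment prematurely".

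The numerator comes from the compliance log. Protocol 8.2.2 has every self-application recorded in it. Protocol Appendix 1 has it dispensed at Visits 2 to 5 and collected at Visits 3 to 6. Protocol 8.2.4 says of the Week 2 visit: "Patients will be required to provide the patient compliance log for confirmation of compliance".

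Neither document adjusts the expected count for actual visit dates or for an early-termination visit.

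**The concern.** The numerator covers the days that actually passed between two visits, while the denominator assumes exactly 14 days. A short interval therefore looks like missed applications, and a long one gives a figure above 100%. A patient who stops partway through an interval can be charged for days on which no cream was due.

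The compliance table is where a reader would compare use of the 1%, 5% and vehicle creams. Window scatter mainly adds noise to that comparison. Early stopping only pushes the figure down, so it could make one arm look less adherent when its patients had used the cream as instructed until they stopped. Replacing 14 by 28 repairs the daily count but not this mismatch.

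**Working it through.** **The SAP's own figure.** Twice daily for 14 days is 2 × 14 = 28. The stated 14 is obtained only with one application per day. With 14 in the denominator, a perfect user at nominal visits reads 28/14 = 200%. That is a separate error; everything below uses 28.

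**Applications by a perfect user.** Protocol 10.3 defers the visit-day morning application until the assessments are done, so it is not lost, and puts the last application on the day before Visit 6 or early termination. SAP 2.2.5 gives two applications on Day 0. The count for an interval is therefore 2 × (closing visit day − opening visit day), assuming on-site applications are counted.

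**Effect of the windows.** Compliance = 2 × days / 28 × 100.

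| Interval | Days | Applications | Reading |
|---|---|---|---|
| 1 (Day 0 has no window) | 14 ± 2 = 12 to 16 | 24 to 32 | 85.7% to 114.3% |
| 2, 3 and 4 | 14 ± 4 = 10 to 18 | 20 to 36 | 71.4% to 128.6% |

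**How often.** Assume each visit day is uniform over its five permitted days; the documents give no distribution.

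- Intervals 2 to 4, 25 equally likely pairs: 13/25 = 52% last 13 to 15 days and read 93% to 107%. A further 6/25 = 24% last 12 days or fewer and read 86% or lower, and 24% last 16 days or more. Each extreme has probability 1/25 = 4%.
- Interval 1: 2/5 = 40% are a full two days off and read 86% or 114%.
- If visits scatter by only ±1 day, 2/9 = 22% of intervals 2 to 4 are two days off.

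**Effect of early termination**, if that visit closes the interval. A perfect user whose visit falls k days in reads 2k/28: 21.4% at k = 3, 50.0% at k = 7, 71.4% at k = 10.

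**Arm level.**

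- Windows: each visit day has variance (4 + 1 + 0 + 1 + 4)/5 = 2, so the length of intervals 2 to 4 has SD √4 = 2 days, or 2/14 = 14.3%. With 100 patients per arm (Protocol 6.1), the standard error is 14.3/√100 = 1.4 points around a mean of 100%.
- Early stopping: 5% of an arm stopping mid-interval and reading 50% lowers the mean by 0.05 × (100 − 50) = 2.5 points in that interval.

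**Whole treatment period.** A completer is treated for 54 to 58 days, giving 108/112 = 96.4% to 116/112 = 103.6%. The window errors largely cancel, but the SAP reports compliance by interval only.

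**The case against.** The strongest reply is that this is a descriptive table reported by arm, where window scatter averages out. Blinded sites have no evident reason to time visits differently by treatment. That stands for the windows: the arm mean stays near 100%, and the distortion lies in individual values and their spread.

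A second reply is that the SAP does not say whether an early-termination visit counts as returning to the clinic for the interval. If it does not, the low readings disappear. That also stands, so those figures are conditional. Protocol 8.2.7 handles Week 8 and early termination as one visit at which the log is collected, so the conditional reading is plausible, but the SAP should state it.

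A third reply is that 14-day blocks could be cut from the log, regardless of visits. Then only the last block varies with the window, from 24/28 = 86% to 32/28 = 114%, plus early stops. The clinic-return restriction points to visit-bounded intervals, though this is an inference.

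Finally, measuring use against the full planned regimen is a defensible convention for exposure. It would still need to be stated, and it does not explain readings above 100%.

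**Conclusion.** The point holds as a minor one. With the daily count corrected to 28, per-interval compliance still mixes adherence with visit timing and, under the stated condition, with early stopping.

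Four stronger readings are tempting and are not supported:

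- A reader might infer that adherent patients routinely read 71% or 129%. These need adjacent visits at opposite ends of their windows, and they cannot occur in interval 1.
- A reader might infer that the 5% arm will look less adherent. Nothing in the documents shows that stopping will differ by arm. Protocol 1.6 reports adverse events similar to vehicle in the Phase IIa study, so the 2.5 points is an illustration only.
- A reader might infer that the full-adherence estimand is compromised. In SAP 2.2.6 that estimand rests on the missing-at-random model, and compliance enters none of the efficacy models in SAP 2.2.12.
- A reader might infer that the per-protocol set would be misclassified. SAP 2.2.4.3 defines it by completion without major violations and states no compliance cut-off. The point would carry more weight only if such a cut-off were later based on this measure.

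**What to change.** Replace the fixed count in SAP 2.2.13.1 with these rules:

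- Expected applications = 2 × (closing visit date − opening visit date).
- If discontinuation of cream within the interval is documented: 2 × (last application date − opening visit date + 1). The added day matters. With an interval opening on Day 14 and a last evening application on Day 16, a perfect user makes 6 applications. The formula expects 2 × 3 = 6; without the added day it would expect 4 and read 150%.
- Do not truncate for patients without documented discontinuation. Otherwise someone who quietly stops and attends the next visit could read 100%.
- State that an early-termination visit closes an interval.
- Add an overall per-patient figure on the same basis, and report treatment duration separately so that early stopping stays visible.

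A perfect user then reads 100% in every interval, whatever the visit dates. The cost is a few lines of SAP text and slightly more programming. The visits are dated, the log exists, and SAP 2.2.13.1 already collects first and last application dates. The downside is that compliance no longer reflects early stopping, which is why duration must be shown beside it.
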